4.1.1.2.3. Early Discontinuation of Treatment Visit

Participants unable or unwilling to continue the study treatment for any reason will perform an early discontinuation (ED) of treatment visit (Section 7.1). If the participant is discontinuing during an unscheduled visit or a scheduled visit, that visit should be performed as an ED visit. Procedures should be completed according to the SoA. Patient-reported outcomes questionnaires should be administered as early as possible, as per Suggested Visit Structure (Section 10.8). Administration of Mental Health questionnaires should follow assessment for AEs.

4.1.1.3. Safety Follow-up Period

Visit 801

All participants are required to complete a safety follow-up visit (Visit 801), according to the SoA. Participants discontinuing the study early and performing an ED visit will also be asked to perform the safety follow-up visit. During the safety follow-up period, participants will not receive study drug. Participants may be treated with another glucose-lowering intervention at the discretion of the investigator or participant's usual diabetes care physician (see Section 6.5.2). If any new AHM is initiated during the safety follow-up period, it will not be classified as rescue

therapy (see Section 6.5.3.1). Participants are also required to return any remaining study diaries to the study site at the end of this period.

For participants who discontinue or complete the study, Visit 801 (safety follow-up visit) should be performed 4 weeks after the last visit of the treatment period (Visit 21 or 99) or 4 weeks after the ED visit for those who decline to return for Visit 99.

4.1.2. Study Procedures

Participants will perform study procedures listed in the SoA.

Participants will be permitted to use concomitant medications that they require during the study, except certain medications that may interfere with the assessment of efficacy and safety characteristics of the study treatments (Section 5.2).

Study governance considerations are described in detail in Section 10.1 (Appendix 1).

4.2. Scientific Rationale for Study Design

CCI

It is administered QW by SC injection.

As a dual GIP/GLP-1R agonist, tirzepatide could exceed the efficacy of selective GLP-1R analogs by recruiting metabolically active tissues not targeted by selective GLP-1R analogs (for example, adipose tissue as indicated by the observation of increased energy utilization) (Müller et al. 2018) and has the potential to reach higher efficacy in target tissues, such as insulin-producing pancreatic beta-cells that express both GIPR and GLP-1R, before reaching its therapeutic limitation. Results from a Phase 2 study (GPGB) demonstrated that tirzepatide use in participants with T2DM was associated with a substantial, dose-dependent weight loss, greater than the weight change observed with dulaglutide, a specific GLP-1R agonist. General safety characteristics of all studied doses of tirzepatide were similar to that of the GLP-1R agonist class, consisting mainly of nausea, vomiting, and diarrhea. In general, these events were transient and mild or moderate in severity, with few severe episodes. This suggests that tirzepatide has the potential to become a medication for chronic weight management.

Although GI AEs were more common in the 15-mg arm of tirzepatide in the Phase 2 study (GPGB), this dose demonstrated the highest efficacy in terms of weight loss. An optimized dose escalation regimen proposed in the Study GPHL to improve tolerability (and supported by a dose escalation algorithm from study GPGF and PK/PD modelling) should enable a use of higher doses to maximize effects on body weight.

Study GPHL is designed to determine the comparative benefits and risks of tirzepatide 10 mg and 15 mg QW versus placebo in participants with T2DM who have obesity or are overweight. A double-blind design was selected to minimize participant and investigator bias in assessments for efficacy, safety, and study drug tolerability.

A placebo comparator was selected for this trial in accordance with regulatory guidance (FDA 2007; EMA 2016). In addition, all participants, regardless of treatment assignment, will receive lifestyle modification counselling and diabetes education consistent with current guidelines for weight management (Jensen et al. 2014) and T2DM management (ADA 2020). Specifically,

participants will consult with a dietician, or equivalent qualified delegate, throughout the study to achieve approximately a 500 kcal/day energy deficit through a combination of caloric restriction and increased physical activity.

The planned duration of treatment for the primary endpoint at 72 weeks allows for a 52-week treatment period at the dose achieved following dose escalation to either 10 or 15 mg. This duration is considered appropriate to assess the full effects and benefit/risk of each maintenance dose of tirzepatide compared with placebo on body weight and is consistent with regulatory guidelines (FDA 2007; EMA 2016).

The effects of study drug cessation will be assessed in the 4-week safety follow-up/observational period. To minimize the potential confounding effect of changes to concomitant medications, participants will be permitted to use concomitant medications that do not interfere with the assessment of efficacy or safety characteristics of the study treatments.

4.3. Justification for Dose

Dose selection for the tirzepatide program focused on addressing the unmet need of achieving greater than 10% weight loss (Srivastava and Apovian 2018a; Ganguly et al. 2018) in order to provide greater metabolic and functional benefits to people with obesity.

Tirzepatide doses of 10 mg and 15 mg QW will be evaluated in this study. These doses and associated escalation schemes were selected based on assessment of safety, efficacy (weight loss), and GI tolerability data in Phase 1 and 2 studies with T2DM, followed by exposure response modeling of the data that predicted weight loss in patients with overweight or obesity.

In a 26-week, Phase 2 study (GPGB) of participants with T2DM, tirzepatide reduced body weight by 4.8 kg, 8.7 kg, and 11.3 kg at dose levels of 5, 10, and 15 mg, respectively, whereas the weight loss observed in participants on dulaglutide, a selective GLP-1R agonist, used at the dose of 1.5 mg, was 2.7 kg (Frias et al. 2018).

Similar to the GLP-1R agonist class, most of tirzepatide AEs were dose dependent and GI-related, consisting mainly of nausea, vomiting, and diarrhea. In general, these events were mild or moderate in severity, with few severe episodes, and transient.

Tirzepatide doses of 10 mg and 15 mg were selected based principally on the following criteria:

- each dose provides robust weight loss relative to placebo,
- the percent of patients achieving >10% is higher with 15 mg than 10 mg,
- both doses are expected to address the unmet need of achieving greater than 10% weight loss, and
- safety and tolerability of 10 mg and 15 mg were supported by Phase 2 results and/or PK/PD modeling.

Tirzepatide dose of 5 mg is not selected as a maintenance dose since it is unlikely to help address the unmet need of achieving greater than 10% weight loss. This is further supported by the following data from the T2DM Phase 2 Study GPGB:

- only 16.7% of participants on 5 mg achieved $\geq 10\%$ weight loss compared to 45.5% and 54.3% of participants on 10 mg and 15 mg, respectively, in the 26-week on treatment analysis

- patients treated with tirzepatide 5 mg demonstrated a placebo-corrected mean body weight loss of 4.4 kg and mean percentage weight loss of 4.7%
 - among the 4 currently FDA-approved medications for chronic weight management, placebo-corrected mean body weight loss and mean percentage weight loss from baseline range from 2.9 to 8.6 kg and from 2.9% to 8.6%, respectively (Apovian et al. 2015)
 - although there were no head-to-head clinical trials comparing tirzepatide with the current FDA-approved medications for chronic weight management, based on data from GPGB, it is unlikely that tirzepatide 5 mg will demonstrate significant benefit over existing treatment options and address the unmet need of achieving greater than 10% weight loss to provide greater metabolic and functional benefits to people with obesity

To address the decreased tolerability and increased treatment discontinuation in the 15-mg arm observed in GPGB, Lilly conducted the Phase 2 study GPGF to investigate the impact of different starting doses and escalation regimens on tolerability. Slower dose escalation and smaller dose increments are anticipated to improve tolerability. Dosing algorithms starting at a low dose of 2.5 mg accompanied by dose escalation of 2.5 mg increments every 4 weeks should permit time for development of tolerance to GI events and are predicted to minimize GI tolerability concerns. The maximum proposed dose of 15 mg maintains an exposure multiple of 1.6 to 2.4 to the no-observed adverse effect level doses in 6-month monkey and rat toxicology studies.

4.4. End of Study Definition

Section 7.2 describes the criteria used to determine if a participant has completed the study. The end of the study is defined as the date of the last visit of the last participant in the study or last scheduled procedure shown in the SoA for the last participant in the trial globally.

5. Study Population

Prospective approval of protocol deviations to recruitment and enrollment criteria, also known as protocol waivers or exemptions, is not permitted.

5.1. Inclusion Criteria

Participants are eligible to be included in the study only if all of the following criteria apply:

Type of Participant and Disease Characteristics

1. Have a BMI ≥ 27 kg/m²
2. Have a diagnosis of T2DM according to the World Health Organization (WHO) classification or other locally applicable standards (see Section 10.10), with HbA1c $\geq 7\%$ (≥ 53 mmol/mol) to $\leq 10\%$ (86 mmol/mol) at screening, on stable therapy for the last 3 months prior to screening. Type 2 diabetes mellitus may be treated with diet/exercise alone or any **oral** glycemic-lowering agent (as per local labeling) EXCEPT dipeptidyl peptidase 4 (DPP-4) inhibitors or GLP-1R agonists
3. Have a history of at least 1 self-reported unsuccessful dietary effort to lose body weight
4. In the investigator's opinion, are well-motivated, capable, and willing to:
 - perform finger stick BG monitoring, including weekly fasting glucose measurements and scheduled BG profiles with up to 7 measurements in 1 day
 - learn how to self-inject study drug, as required for this protocol (visually impaired persons who are not able to perform the injections must have the assistance of a sighted individual trained to inject the study drug; persons with physical limitations who are not able to perform the injections must have the assistance of an individual trained to inject the study drug)
 - inject study drug (or receive an injection from a trained individual if visually impaired or with physical limitations)
 - follow study procedures for the duration of the study, including, but not limited to follow lifestyle advice (for example, dietary restrictions and exercise plan), maintain a study diary, and complete required questionnaires

Participant Characteristics

5. Are at least 18 years of age and age of majority per local laws and regulations
 - a. Male participants:
 - Male participants with partners of childbearing potential should be willing to use reliable contraceptive methods throughout the study and

for 5 half-lives of study drug plus 90 days, corresponding to 4 months after the last injection

b. Female participants:

- Female participants not of childbearing potential may participate and include those who are:
 - infertile due to surgical sterilization (hysterectomy, bilateral oophorectomy, or tubal ligation), congenital anomaly such as Mullerian agenesis; or
 - postmenopausal – defined as either:
 - A woman at least 40 years of age with an intact uterus, not on hormone therapy, who has cessation of menses for at least 1 year without an alternative medical cause, AND a follicle-stimulating hormone (FSH) ≥ 40 mIU/mL; women in this category must test negative in pregnancy test prior to study entry

or

- A woman 55 or older not on hormone therapy, who has had at least 12 months of spontaneous amenorrhea

or

- A woman at least 55 years of age with a diagnosis of menopause prior to starting hormone replacement therapy (HRT)
- Female participants of childbearing potential (not surgically sterilized and between menarche and 1-year postmenopausal) must:
 - test negative for pregnancy at Visit 1 based on a serum pregnancy test,
 - if sexually active, agree to use 2 forms of effective contraception, where at least 1 form is highly effective for the duration of the trial plus 30 days, corresponding to 2 months after the last injection, and
 - not be breastfeeding

Note: Contraceptive use by men or women should be consistent with local regulations regarding the methods of contraception for those participating in clinical studies.

Informed Consent

6. Capable of giving signed informed consent as described in Appendix 1 which includes compliance with the requirements and restrictions listed in the ICF and in this protocol

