The C-SSRS should be administered after assessment of adverse events. For this study, the C-SSRS is adapted for the assessment of the ideation and behavior categories only. The Intensity of Ideation and Lethality of Behavior sections are removed.																								
Columbia-Suicide Severity Rating Scale (C-SSRS) (Since Last Visit Version)		X	X	X	X	X	X	X	X	X	X	X	X	X	X	X	X	X	X	X	X	X	X	X
The C-SSRS should be administered after assessment of adverse events and capture information since most recent C-SSRS administration. For this study, the C-SSRS is adapted for the assessment of the ideation and behavior categories only. The Intensity of Ideation and Lethality of Behavior sections are removed.																								
Self-Harm Supplement Form	X	X	X	X	X	X	X	X	X	X	X	X	X	X	X	X	X	X	X	X	X	X	X	X
The Self-Harm Supplement Form should be administered after assessment of adverse events.																								
Self-Harm Follow-up Form	X	X	X	X	X	X	X	X	X	X	X	X	X	X	X	X	X	X	X	X	X	X	X	X
Self-Harm Follow-up Form is only required if triggered by the Self-Harm Supplement Form, per instructions in the form.																								
Laboratory Tests and Sample Collections																								
Hematology	X					X			X													X		X
HbA1c	X		X			X			X			X			X			X			X		X	X

Visit	1	2	3	4	5	6	7	8	9	10	11	12	13	14	15	16	17	18	19	20	21	99	ED	801	
Week of Treatment	-3	-2	0	4	8	12	16	20	24	28	32	36	40	44	48	52	56	60	64	68	72	72			4 wks post end of TxP
Allowable Interval Tolerance (days)		±3	±7	±3	+7	±3	+7	±3	±3	±3	±3	+7	±3	±3	±3	±3	±3	±3	±3	±3	±7	±7			±3
Fasting Visit	X		X	X	X	X	X	X	X			X			X			X			X	X	X	X	X
Telephone Visit										X	X		X	X		X	X		X	X					
Chemistry panel (includes Creatinine for eGFR calculation and glucose)	X		X			X			X			X			X			X			X		X	X	X
	The CKD-EPI equation will be used by the central lab to estimate and report eGFR.																								
Lipid panel	X		X						X														X	X	X
Insulin			X						X														X	X	X
C-peptide			X						X														X	X	X
Free fatty acids	X		X						X														X	X	X
Serum pregnancy	X																								
	For women of childbearing potential only																								
Urine pregnancy (local)			X			X			X			X			X			X				X		X	

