10.5. Appendix 5: Contraceptive Guidance and Collection of Pregnancy Information

Definitions

Woman of Childbearing Potential:

A woman is considered fertile following menarche and until becoming postmenopausal unless permanently sterile (see below).

If fertility is unclear (for example, amenorrhea in adolescents or athletes) and a menstrual cycle cannot be confirmed before first dose of study intervention, additional evaluation should be considered.

Women in the following categories are not considered women of childbearing potential:

Article I. Premenarchal

Article II. Premenopausal female with 1 of the following:

- Documented hysterectomy
- Documented bilateral salpingectomy
- Documented bilateral oophorectomy

For individuals with permanent infertility due to an alternate medical cause other than the above, (for example, Mullerian agenesis, androgen insensitivity), investigator discretion should be applied to determining study entry.

Note: Determination can come from the site personnel's: review of the participant's medical records, medical examination, or medical history interview.

Article III. Postmenopausal female:

- A postmenopausal state is defined as either:
 - A woman at least 40 years of age with an intact uterus, not on hormone therapy, who has cessation of menses for at least 1 year without an alternative medical cause, AND a FSH \geq 40 mIU/mL; or
 - A woman 55 or older not on hormone therapy, who has had at least 12 months of spontaneous amenorrhea; or
 - A woman at least 55 years of age with a diagnosis of menopause prior to starting HRT.
- Females on HRT and whose menopausal status is in doubt will be required to use 1 of the non estrogen hormonal highly effective contraception methods if they wish to continue their HRT during the study. Otherwise, they must discontinue HRT to allow confirmation of postmenopausal status before study enrollment.

Contraception Guidance

Contraceptive use by men and women should be consistent with local regulations regarding the methods of contraception for those participating in clinical studies.

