Two forms of effective contraception, where at least 1 form is highly effective, will be used. Effective contraception may be used as the second therapy. Barrier protection methods without concomitant use of a spermicide are not a reliable or acceptable method. The use of male and female condoms as a double barrier method is not considered acceptable due to the high failure rate when these methods are combined.

Highly Effective Methods of Contraception:

- Combined oral contraceptive pill and mini pill
- NuvaRing
- Implantable contraceptives
- Injectable contraceptives (such as Depo-Provera[®])
- Intrauterine device (such as Mirena[®] and ParaGard[®])
- Contraceptive patch – ONLY women <198 pounds or 90 kg
- Total abstinence (if this is their preferred and usual lifestyle) or in a same-sex relationship with no sexual relationship with males (as part of their preferred and usual lifestyle), and agrees to maintain this status throughout trial follow-up

Note: Periodic abstinence (for example, calendar, ovulation, symptothermal, and postovulation methods), declaration of abstinence just for the duration of a trial, and withdrawal are not acceptable methods of contraception.

- Vasectomy – for men in clinical studies

Note: Implantable contraceptives and injectable contraceptives (such as Depo Provera) are only permitted if started more than 18 months prior to screening. Participants should not start these methods of contraception after being enrolled in the study.

Effective Methods of Contraception (must use combination of 2 methods):

- Male condom with spermicide
- Female condom with spermicide
- Diaphragm with spermicide
- Cervical sponge
- Cervical cap with spermicide

Men, regardless of their fertility status, with nonpregnant WOCBP partners must agree to either remain abstinent (if this is their preferred and usual lifestyle) or use condoms plus 1 additional highly effective (less than 1% failure rate) method of contraception (such as combination oral contraceptives, implanted contraceptives, or intrauterine device) or effective method of

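### Criterion 5b and Appendix 5 give a woman with tubal ligation opposite childbearing status, and no scheduled test matches 5b's pregnancy-test clause for the FSH-defined postmenopausal group

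*Protocol*

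**What the plan says.** Protocol Section 5.1, criterion 5b, admits women not of childbearing potential and gives surgical and congenital routes into that class. The surgical route covers women who are "infertile due to surgical sterilization (hysterectomy, bilateral oophorectomy, or tubal ligation"; the congenital route names Mullerian agenesis, and the postmenopausal definitions follow. It describes the complementary group in the same terms: "Female participants of childbearing potential (not surgically sterilized and between menarche and 1-year postmenopausal) must" have a negative serum test at Visit 1 and, if sexually active, use two forms of contraception, at least one of them highly effective.

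One postmenopausal subgroup in 5b is defined by age of at least 40, an intact uterus, no hormone therapy, at least a year without menses and FSH of 40 mIU/mL or more. It carries an extra condition: "women in this category must test negative in pregnancy test prior to study entry".

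Section 10.5 (Appendix 5) starts from the presumption that a woman is fertile from menarche to menopause unless permanently sterile. For premenopausal women it names three qualifying operations: hysterectomy, bilateral oophorectomy and a third item, "Documented bilateral salpingectomy". Tubal ligation is not named. Permanent infertility from other medical causes, with Mullerian agenesis as an example, is left to the investigator's discretion on study entry. Appendix 5 repeats the FSH-defined subgroup without a pregnancy test.

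The Schedule of Activities (Section 1.3) has a serum test at Visit 1, annotated "For women of childbearing potential only", and a urine test from Visit 3 with the same restriction. It does not define the term.

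**The concern.** Whether a woman counts as being of childbearing potential decides whether she is tested before the first injection, whether she is retested over 72 weeks on an investigational drug, and whether she must use contraception. If two sections of one protocol classify her differently, sites will handle identical women differently, and monitors will have no agreed standard against which to call a deviation.

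The FSH subgroup raises a separate problem of execution. An entry condition with no matching scheduled procedure is easily missed, and Section 5 permits no waivers of enrollment criteria. Pregnancy on study also ends both treatment and participation (Section 7.2 and Appendix 5), so the classification bears on retention as well as on safety.

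**Working it through.** No arithmetic is needed to establish the point, and the plan states no figure to reproduce. The check is to take each type of woman through the three places.

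| Woman | Criterion 5b | Appendix 5 | Schedule of Activities |
|---|---|---|---|
| Premenopausal, tubal ligation | Surgically sterilized, so not of childbearing potential | Not on the list of operations, so fertile by default | Tests only if of childbearing potential; term undefined |
| Mullerian agenesis | Automatically not of childbearing potential | Study entry at investigator discretion | As above |
| Age at least 40, amenorrhea, FSH at least 40 mIU/mL | Not of childbearing potential, but must test negative before entry | Not of childbearing potential; no test mentioned | FSH row calls her postmenopausal; pregnancy rows do not reach her |

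**Tubal ligation.** Under 5b she falls outside the group with test and contraception duties, so the Schedule's pregnancy rows do not apply. Under Appendix 5 she falls inside it. The Schedule then gives her the Visit 1 serum test, a urine test at Visit 3 before the first injection and further urine tests about every 12 weeks. The contraception rule also applies: "Two forms of effective contraception, where at least 1 form is highly effective, will be used". Criterion 5b limits its own version of that duty to women who are sexually active. The Appendix 5 lists of methods do not include female sterilization (only vasectomy, for men), so her ligation does not count there even as one of the two forms.

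**Does another passage settle it?** Criterion 5b does not cite Appendix 5 for the definition. Appendix 2 points to Section 5.1, but only for screening pregnancy criteria and not for on-study testing or contraception. The Appendix 5 clause on other causes of permanent infertility concerns study entry and does not state childbearing status. The conflict remains.

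**Mullerian agenesis.** This is the same kind of mismatch: automatic in one place, discretionary in the other.

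**FSH subgroup.** The disagreement is about testing only. Neither 5b nor Appendix 5 imposes contraception on these women. Criterion 5b demands a negative result, and no row of the Schedule orders the test that would supply it.

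**Size.** The only related figures in the documents are the planned 900 participants and the 70% ceiling on women, so at most 0.70 × 900 = 630 women. Neither document gives the share who are premenopausal, have had a tubal ligation or fall in the FSH subgroup. Any count of affected women would be the product of assumed shares and an enrollment ceiling, so none is offered.

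**The case against.** The strongest reply is that eligibility is governed by Section 5.1, which plainly admits women with tubal ligation. A site following it commits no eligibility deviation. The Schedule also asks for extra pregnancy tests whenever a period is missed or pregnancy is suspected, which is a safety net throughout treatment. Both points are right and they limit the consequences. They do not reconcile the two definitions for scheduled testing and contraception after entry.

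A reader might infer several stronger things that the documents do not support.

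- *That a site following the Schedule cannot satisfy the FSH-subgroup clause.* Appendix 2 refers sites to Section 5.1 for screening pregnancy criteria and allows additional tests at the investigator's judgment. FSH and the serum test are both Visit 1 samples, so a woman's status may not be known when blood is drawn and she may well be tested. What stands is that no scheduled row orders the test.
- *That bilateral salpingectomy is a second contradiction.* The list in 5b is introduced as inclusive, and 5b's own description of childbearing potential excludes anyone surgically sterilized. Salpingectomy fits without being named.
- *That the Appendix 5 heading "Effective Methods of Contraception (must use combination of 2 methods" makes two merely effective methods enough for women.* The requirement for at least one highly effective form is explicit in both Section 5.1 and Appendix 5. Appendix 5 also lets male participants combine condoms with an effective method, so the heading has a legitimate use.
- *That the Schedule defines childbearing potential differently.* It does not define it at all.
- *That undetected fetal exposure will follow.* Given the extra-test instruction, this is a risk to be reduced, not a demonstrated outcome.

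**Conclusion.** The point holds as an internal inconsistency in the protocol. For a premenopausal woman with tubal ligation it is a full contradiction: scheduled tests and two contraceptive methods under Appendix 5, neither under criterion 5b. For Mullerian agenesis the conflict is between automatic classification and investigator discretion. For the FSH subgroup it is narrower: a required negative test that nothing in the Schedule orders.

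The tubal-ligation conclusion assumes that the operations listed in Appendix 5 are meant to be complete for surgical causes, which is how that list is worded. The number of women affected cannot be derived from the documents. Sample size, alpha, power and the planned analyses are unaffected. It should be corrected because it bears on participant safety and costs little, but it does not threaten the trial's conclusions.

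**What to change.** State one definition of childbearing potential once, with one list of sterilization procedures and one rule for congenital causes such as Mullerian agenesis. Refer to it from criterion 5b, Appendix 5 and the pregnancy-test rows of the Schedule of Activities. Make the Schedule's serum-test note and the 5b clause on the FSH-defined subgroup agree on whether that group is tested at screening. The sponsor's medical team decides which version stands; the statistical review has no view on the clinical rule.

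The cost is amendment wording and site notification, plus a few more or fewer pregnancy tests depending on the version chosen. No analysis changes.
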